### **Angiographic Exclusion Criteria**

13. The subject has extensive peripheral vascular disease, which in the opinion of the Investigator, would preclude safe insertion of an introducer sheath. The ipsilateral common femoral artery should be patent (< 50% stenosis) by the Investigator's visual estimate.
14. The target lesion(s) requires treatment other than angioplasty (e.g., atherectomy, cryoplasty, cutting/scoring balloons, etc.) to facilitate subject device delivery. Devices such as CTO catheters or re-entry devices may be used to facilitate target lesion(s) crossing.
15. The subject has severe calcification of the target lesion(s), which prevents inflation of a PTA balloon (pre-dilatation of the target lesion is required).
16. The target lesion(s) has been previously treated with a stent (bare or covered). A target vessel(s) with a previously placed stent is permitted as long as the subject device(s) will not come into contact with the previously placed stent during treatment of the target lesion(s).
17. The subject has angiographic evidence of acute thrombus at the target lesion(s).
18. The target lesion(s) involves the origin of the internal iliac artery such that successful treatment of the lesion(s) would require the subject device(s) to cross/occlude the side branch. Note, if the internal iliac artery is already occluded, the subject device(s) can be placed across the occluded vessel.
19. The target lesion(s) is (are) located in the distal external iliac artery such that successful treatment of the lesion(s) would require the subject device(s) to cross/occlude side branches (inferior epigastric artery and/or deep circumflex iliac artery) or be exposed to compressive forces associated with the close proximity to the common femoral artery. Note, if the side branch(es) is (are) already occluded, the subject device(s) can be placed across the occluded vessel(s) as long as the device is above the inguinal ligament.

20. The subject has an abdominal aortic aneurysm (AAA) contiguous to the iliac artery target lesion(s). The presence of AAA grafts and/or endografts are not permitted.
21. The subject has a pre-existing target iliac artery aneurysm or perforation or dissection of the target iliac artery prior to the initiation of the treatment for this study.

## **5. STUDY PROCEDURES**

Prior to the conduct of any study procedures, the subject must voluntarily provide consent and comply with applicable national and state privacy laws (e.g., HIPAA requirements in the U.S.). All study procedures will be documented in the medical record and/or source document and on study electronic case report forms (eCRFs).

See Appendix 1 for the Time and Events Schedule of study procedures.

### **5.1. Subject Screening and Baseline Evaluation**

During the screening, the investigator (or authorized designee) will be responsible for describing the nature of the study, verifying that the eligibility criteria have been met, and obtaining informed consent. Prior to the conduct of any study procedures, the subject must voluntarily provide consent and comply with applicable national and state privacy laws (e.g., HIPAA requirements in the U.S.). All study procedures will be documented in the medical record and/or source document and on study eCRFs.

The following specific procedures will be conducted and documented:

#### **5.1.1. Informed Consent**

All subjects will provide written informed consent for the study prior to collection of study data or performance of study-related procedures (See Section 11.4). The ICF templates are stand-alone documents to facilitate revision(s), as necessary, without requiring a protocol amendment. Documentation of the Informed Consent process must be present in the medical record and/or source document.

#### **5.1.2. Eligibility**

The subject's eligibility for study enrollment will be reviewed and documented, and a related progress note should indicate that the subject met all study (eligibility) criteria at the time of screening and enrollment.

#### **5.1.3. Demographics and Medical History**

The subject's demographic information will be obtained, including:

- Date of Birth (minimum year of birth)
- Sex
- Cardiovascular History

- History of risk factors
- Previous interventions (e.g., interventional and/or surgical; coronary and/or peripheral)

#### **5.1.4. Baseline Examinations**

Each subject will have the following baseline examinations performed prior to the index procedure:

- Review of concomitant medications (antiplatelets, anticoagulants, direct thrombin inhibitors, and factor Xa inhibitors) taken within 72 hours prior to index procedure
- Comprehensive physical examination of the subject's overall health status conducted within 30 days prior to index procedure, including Height and Weight
- Urine or blood pregnancy test for women of childbearing potential within 14 days prior to index procedure (to confirm eligibility criteria only)
- Laboratory testing including Blood Urea Nitrogen (BUN) or Creatinine and Complete Blood Count (CBC), including Platelets, within 30 days prior to index procedure (to confirm eligibility criteria only)
- Comprehensive physical examination of the subject's vascular status conducted within 30 days prior to index procedure, including:
  - Resting bilateral ABIs
  - Target Limb Assessment
  - Rutherford Category & Grade Assignment
- Quality of Life Assessment
  - WIQ to be completed within 30 days prior to index procedure

#### **5.1.5. Clinical Evaluations**

Please refer to the site regulatory binder for detailed information on the standard guidelines/instructions for clinical evaluations such as ABI, DUS, and completion of the WIQ.

#### **5.1.6. Procedural Medications**

During the index procedure, it is recommended that subjects receive intravenous (IV) heparin or bivalirudin, as per the institutional standard of care. If the subject is not currently taking clopidogrel, a loading dose of 300 mg – 600 mg (oral) should be administered at the time of the index procedure, or immediately following successful intervention. Ticlopidine may be administered if the subject has an allergy or contraindication to clopidogrel. Clopidogrel is not required if a subject is taking warfarin, prasugrel, ticagrelor, and/or approved direct thrombin inhibitors (e.g., dabigatran) or factor Xa inhibitors (e.g., rivaroxaban, apixaban). The total amount of heparin (bivalirudin) or clopidogrel (ticlopidine) that is administered during the index procedure should be documented.

If the subject is diabetic, it should be documented whether the subject is on insulin, oral agents, or a dietary regiment for treatment.

### 5.1.7. Diagnostic Angiogram

Prior to any study intervention, subjects meeting the clinical eligibility criteria for the study will undergo diagnostic angiography to better characterize the degree of atherosclerosis and ensure that the subject meets all angiographic inclusion and exclusion criteria.

Access should be gained per the institution's standard technique. The procedure begins at the time that arterial access is obtained.

All angiography shall be performed using the identical angles, magnification and angiographic technique as described in the "Angiography Guidelines" supplied by the Angiographic Core Lab. **It is important to use the specified calibrated measurement catheter so that the Angiographic Core Lab may properly assess the target lesion characteristics (e.g., reference vessel diameter, lesion diameter and length). Properly labeled angiographic-recorded media are to be uploaded or sent to the Angiographic Core Lab for evaluation.**

## 5.2. Index Procedure

Preparation should be conducted adhering to the site's standard of care for procedures and monitoring, including the use of standard sterile operative techniques.

### 5.2.1. Target Lesion(s) PTA

All subjects will undergo conventional PTA pre-dilatation at the target lesion site(s) previously identified by angiography. Prior to PTA, the Investigator shall identify (by visual estimation) the beginning and end of each target lesion(s). The target lesion(s) should have a combined (single or multiple lesions) **lesion length of less than or equal to 100 mm per side** (unilateral or bilateral disease). PTA shall be limited to predetermined treatment segment(s).

**It is required that angiographic image(s) of the inflated PTA balloon be captured.**

Choice of specific balloon catheters and inflation pressure should be determined by the Investigator based on his/her standard of care practices, and should be recorded. It is **not** acceptable for the Investigator to use additional commercially-approved treatment modalities (e.g., atherectomy, cryotherapy, cutting/scoring balloon) during the study procedure. Subjects who require treatment with any of these alternative modalities should not be enrolled in the study. It is acceptable for the Investigator to use CTO catheters or re-entry devices to facilitate target lesion(s) crossing.

In certain instances, a dissection may occur following PTA of the target lesion(s).

#### Target Lesion including Dissection: Less than or equal to 100 mm

- If a flow-limiting dissection occurs, and extends beyond the target lesion(s), but the total length of the target lesion(s) plus the dissected segment is less than or equal to 100 mm in length, the LIFESTREAM™ Covered Stent(s) may be used to properly treat the dissected segment.

Target Lesion including Dissection: Greater than 100 mm

- If the total length of the target lesion(s) plus the dissected segment extends greater than 100 mm, the Investigator should **not** place the LIFESTREAM™ Covered Stent(s) to treat the dissected segment. The Investigator should use standard of care practices to treat the dissected segment. As the study device will **not** be introduced, these subjects requiring treatment of dissected segments extending greater than 100 mm will be treated as an intra-procedure screen failure and will not be included in the ITT analysis.

Dissection including the internal iliac (hypogastric) artery or other important collaterals

- If a dissection occurs at the origin of the hypogastric artery (or other important collateral), the Investigator should **not** place the LIFESTREAM™ Covered Stent(s) to treat the dissected segment. The Investigator should use standard of care practices to treat the dissected segment, which may include placing an approved iliac bare metal stent in order to treat the dissection without occluding the hypogastric (or collateral) artery. As the study device will **not** be introduced, these subjects will be treated as an intra-procedure screen failure and will not be included in the ITT analysis. However, if the hypogastric (or collateral) artery is already occluded and the lesion (including dissection) is less than or equal to 100 mm in length, the LIFESTREAM™ Covered Stent(s) may be used to properly treat the dissected segment as long as the device is above the inguinal ligament.

## 5.2.2. Enrollment

### Enrollment

A subject is considered enrolled in the study once he/she has agreed to study participation and has provided consent (an estimated 308 subjects assuming a 50% screen failure rate). Subjects who fail to meet eligibility criteria should be treated according to the Investigator's standard of care practices. Such subjects' study participation will end at the time of eligibility failure.

### Treated Subject

After the subject has met all eligibility criteria, undergone successful PTA of the target lesion(s), and the LIFESTREAM™ Covered Stent catheter is introduced (i.e., delivery system enters the subject's body), the subject will be considered to be a treated subject in the study. Treated subjects will continue study participation through the study's 36-month follow-up period. Subjects that do not receive the LIFESTREAM™ Covered Stent implant (but the LIFESTREAM™ Covered Stent catheter was introduced) will be followed through the 30-day follow-up visit to assess any safety events and will be included in the ITT and PP analyses (see Section 6).

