#### **5.2.4. Intra-Procedure – Other Treatment Modalities**

If the entirety of the lesion(s) cannot be treated to an angiographically acceptable result, consideration should be given to other medically-appropriate treatment modalities, in each case, as dictated by clinical circumstances, institutional standard of care, and Investigator preference. All subjects that receive a LIFESTREAM™ Covered Stent and undergo other treatment modalities will be followed per protocol specifications, will be documented, and included in the ITT analysis. If a subject is converted to bypass surgery and the LIFESTREAM™ Covered Stent is explanted, then the subject will be followed through the 30-day follow-up visit to assess any safety events and will also be included in the ITT. An emergent intervention of any kind is allowed at any time at the discretion of the Investigator, and should be documented in the medical record/source documents.

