## 5.4. Subject Follow-Up

All treated subjects who receive a LIFESTREAM™ Covered Stent will be followed at 30-days and 6-, 9-, 12-, 24-, and 36-months post-index procedure.

---

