## 5.5. Subject Discontinuation

The follow-up period for this study is 36 months (1095 Days  $\pm$  30 Days). Subjects may be discontinued for the following reasons:

- Lost to Follow-Up (LTF): A subject may be considered LTF if the site personnel are unable to locate the subject despite two documented attempts to notify the subject via telephone and a third attempt by certified mail. Before the site considers a subject LTF, written agreement should be obtained from Bard.
- Withdrawn Consent: The subject requests to terminate his/her participation in the study (the Investigator, or authorized designee, must attempt to identify and document the reasons for termination).
- Death: The subject becomes deceased. If known, the cause of death should be documented.
- Withdrawal by Investigator: Participation may be immediately terminated by the Investigator if, in the opinion of the Investigator, the subject would be exposed to inappropriate risk by continuing in the study. Additionally, the Investigator may terminate a subject’s participation with prior written approval from Bard if the subject is repeatedly noncompliant with study procedures.
- Study Termination: The study is terminated by Bard. (See Section 16)

Additional subjects will not be enrolled to replace those who withdraw from the study.

---

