## 6. STATISTICAL ANALYSIS PLAN

### 6.1. Analysis Populations

The ITT population consists of those subjects who have signed the Informed Consent Form and had the LIFESTREAM™ Covered Stent catheter introduced (i.e., delivery system enters the subject's body).

Subjects who do not receive the study implant (section 5.2.2), but the LIFESTREAM™ Covered Stent catheter was introduced will be included in the ITT population. Subjects who need more than two (2) LIFESTREAM™ Covered Stents (section 5.2.3) or undergo other treatment modalities (section 5.2.4) will be included in the ITT population.

A per-protocol (PP) population may be created if there are subjects who have any major protocol deviations. Major Protocol Deviations are defined as those that occur to protect the life or physical well-being of a subject in an emergency, or those that may affect the scientific soundness of the study, or the rights, safety or welfare of human subjects. The PP population will consist of any subjects in the ITT population who do not have any major protocol deviations, including deviations of study eligibility criteria. Subjects who do not receive the study implant (section 5.2.2), but the LIFESTREAM™ Covered Stent catheter was introduced will be included in the PP population. Subjects who need more than two (2) LIFESTREAM™ Covered Stents and require placement of a commercially-available stent (section 5.2.3), or undergo other treatment modalities (section 5.2.4) will be excluded from the PP population.

All effectiveness and safety analyses including the primary analysis will be primarily based on the ITT population. A PP analysis may also be performed for the primary endpoint. It will only serve as a sensitivity analysis for the primary analysis which is based on the ITT population.

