### 6.2. Primary Endpoint: Study Hypothesis

The primary endpoint of the study is a composite safety and effectiveness measure defined as device and/or procedure-related death or MI through 30 days or any TLR, target limb(s) major amputation, or restenosis through 9 months post-index procedure.

The BOLSTER study is a single-arm study of treated subjects receiving the LIFESTREAM™ Covered Stent compared to a PG derived from published literature of stents for the treatment of iliac artery stenosis/occlusion. Specifically, the PG rate was derived as 19.5%.

The primary endpoint will be evaluated by the following hypothesis:

H0: The proportion of subjects in the LIFESTREAM™ Covered Stent group (PBBX) with events in the primary endpoint is greater than or equal to that of the PG of 19.5%.

H1: The proportion of subjects in the LIFESTREAM™ Covered Stent group (PBBX) with events in the primary endpoint is less than that of the PG of 19.5%.

$$\mathbf{H_0: P_{BBX} \geq 19.5\% \quad \text{vs.} \quad H_1: P_{BBX} < 19.5\%}$$

A one-sided p-value will be derived based on an exact binomial test. The study device will be considered to have achieved the primary objective if the one-sided p-value is less than 0.0335 at interim analysis or 0.0325 at final analysis (see section 6.8).

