## 6.6. Handling of Missing Data

Study endpoints may be missing due to withdrawal of consent, investigator's decision, lost to follow-up and death. As long as the missing data is unrelated to the study intervention and the observed and unobserved data, limiting the analysis to those subjects who contribute endpoints produces unbiased estimates of the event rates.

Additionally, Kaplan-Meier survival analyses will be performed to estimate the event rates at various time-points. In survival analyses, unobserved endpoints are a standard part of the analysis. They are known as censored observations.

The reason for missing data for all subjects will be reported. If there is any indication that missing data is related to the study intervention, a worst-case analysis may be performed in addition to the standard analysis. In a worst-case analysis, a failure of effectiveness or safety will be assumed to have occurred at the time the subject was censored.

In addition, regardless of whether missing data are related to the study intervention, a tipping-point analysis will be performed, in which assumptions about missing data are varied from worst-case to best-case to examine at what point the missing data would alter the results of the analysis.

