**APPENDIX 1: Time and Events Schedule**

Observation	Baseline/ Screening	Index Procedure	Hospital Discharge 	30 d  (± 7d)	6 mo  (± 30d)	9 mo (± 30d)	12, 24, & 36 mo (± 30d)
Eligibility Criteria	✓	✓					
Informed Consent	✓						
Demographics	✓						
Medical History	✓						
Pregnancy test	✓ 						
Labs (BUN or Creatinine, CBC including Platelets)	✓						
Concomitant Medications	✓	✓	✓	✓	✓	✓	✓
Comprehensive Physical Exam	✓		✓	✓		✓	✓
Angiogram	✓ 	✓ 					
Resting ABI	✓			✓		✓	✓
Rutherford (Category & Grade)	✓			✓		✓	✓
Adverse Event Assessment		✓	✓	✓	✓	✓	✓
TLR/TVR Assessment				✓ 	✓ 	✓ 	✓ 
Color Flow Duplex Ultrasound				✓ 		✓ 	✓ 
WIQ	✓ 			✓		✓	✓

Subjects meeting the criteria for deployment failure will be evaluated at hospital discharge and the 30-day follow-up visit to assess and document any AEs or SAEs that may have occurred since the index procedure.

Telephone Screen

Perform pregnancy test (urine or blood) for women who are of childbearing potential ≤ 14 days prior to the index procedure.

Send images to Angiographic Core Laboratory

Send images to Ultrasound Core Laboratory

Complete WIQ ≤ 30 days prior to the index procedure

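### The documents conflict on whether ITT subjects with no study implant, or with the stent explanted at bypass, are followed past day 30; if the specific rules govern, some have no scheduled 9-month primary outcome.

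*Combined protocol and SAP*

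**What the plan says.** **Text that stops at day 30.** Section 5.2.2 covers subjects with the catheter introduced but no implant ("will be followed through the 30-day follow-up visit to assess any safety events and will be included in the ITT and PP analyses"). Section 5.2.4 covers conversion to bypass with explant: "then the subject will be followed through the 30-day follow-up visit to assess any safety events and will also be included in the ITT". Section 5.4 ties the later visits to receipt of the device: "All treated subjects who receive a LIFESTREAM™ Covered Stent will be followed at 30-days" and at the visits after that. Footnote 1 of Appendix 1 agrees: "Subjects meeting the criteria for deployment failure will be evaluated at hospital discharge and the 30-day follow-up visit".

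**Text that goes further.** The Design and Procedures rows of the Clinical Protocol Summary, and Section 2, schedule visits through 36 months, including month 9, for all treated subjects. Section 5.2.2 defines a treated subject by catheter introduction, which takes in no-implant subjects, and says that treated subjects stay in the study for 36 months. Section 16 keeps treated subjects in follow-up for 3 years even if the study is terminated.

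**Analysis.** Section 6.1 includes no-implant subjects in ITT and states: "All effectiveness and safety analyses including the primary analysis will be primarily based on the ITT population". The primary endpoint in Section 6.2 counts "any TLR, target limb(s) major amputation, or restenosis through 9 months post-index procedure".

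**Missing data.** Section 6.6 ("Study endpoints may be missing due to withdrawal of consent", followed by investigator's decision, loss to follow-up and death) treats analysis of subjects with observed endpoints as unbiased if missingness is unrelated to the intervention and to the data. It adds Kaplan-Meier analyses, a worst-case analysis that may be done, and a tipping-point analysis that will be done. Section 5.5 ("Subjects may be discontinued for the following reasons") lists five reasons; ending follow-up because there was no implant or an explant is not among them.

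**The concern.** An ITT analysis of a 9-month endpoint needs a 9-month status for each ITT member. Under the day-30 sentences, an affected subject with no event by then leaves with that status unknown, because the protocol schedules no later visit. Event collection under Section 7 also runs only to the final follow-up visit.

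The reason for the gap matters more than its likely size. These subjects are defined by failure to implant or to retain the study device, so the missingness may well be related to the intervention. That is the situation in which Section 6.6's argument for complete cases does not apply. The plan also does not say whether these subjects enter the denominator of the exact binomial test, or how they are scored.

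**Working it through.** **1. Reproducing the design.** Inputs: goal 19.5%, assumed rate 10.5% and 139 evaluable (Section 6.7); one-sided limits 0.0335 at 93 evaluable and 0.0325 at 139 (Section 6.8). Exact binomial tail probabilities at 19.5%:

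- Interim: P(X ≤ 10 of 93) = 0.0178; P(X ≤ 11 of 93) = 0.0356. Success needs at most 10 events.
- Final: P(X ≤ 18 of 139) = 0.0284; P(X ≤ 19 of 139) = 0.0474. Success needs at most 18 events.

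P(success) = P(X₁ ≤ 10) + Σ over x = 11 to 18 of P(X₁ = x) · P(X₂ ≤ 18 − x), with X₁ from 93 and X₂ from the other 46 subjects. This gives 3.65% at a true rate of 19.5% and 86.9% at 10.5%. Table 2 gives 3.8% and 87.1% by simulation, so the rule is reproduced.

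**2. Leaving out subjects with unknown status.** That the primary test uses complete cases is inferred from Section 6.6 and from the evaluable counts in Section 6.8. Three inputs are assumptions, because the documents give none of them: f, the share of affected subjects; q, their 9-month event rate; e, the share of affected subjects whose event is seen by day 30. Holding the true ITT rate at 19.5%:

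- rate in the other subjects: π = (0.195 − f·q)/(1 − f)
- rate among evaluable subjects: r = (f·e + (1 − f)·π)/(f·e + 1 − f)

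Example: f = 2%, q = 0.5, e = 0 gives π = (0.195 − 0.010)/0.98 = 0.1888 = r, and P(success) = 5.24%.

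| Affected subjects | f = 1% | f = 2% | f = 3% |
|---|---|---|---|
| Half have events, all by day 30 | 3.44% | 3.24% | 3.05% |
| Same rate as the rest, none by day 30 | 3.65% | 3.65% | 3.65% |
| Half have events, half of those by day 30 | 3.9% | 4.1% | 4.4% |
| Half have events, none by day 30 | 4.4% | 5.2% | 6.3% |
| Extreme: all have events, none by day 30 | 5.8% | 9.1% | 13.9% |

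With no event seen by day 30, the rate in these subjects must reach about 73%, 46% or 37% (f = 1%, 2%, 3%) before the error passes 5%. These shares are about 1.5 to 4.6 of 154 subjects, against a censoring allowance of 154 − 139 = 15.

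**3. At the boundary.** 18/139 passes (p = 0.0284). One more subject counted as a failure gives 19/140, p = 0.0437, which fails; counted as a success, 18/140 gives p = 0.0260. This holds for any missing subject. The chance of reaching the final analysis and ending exactly at 18/139 is 5.3% at a true rate of 10.5% and 7.9% at 12.5%.

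**4. Effect of restoring these subjects.** Dividing 93 and 139 by 1 − f and rounding up gives 94/141, 95/142 and 96/144, with limits of 11/18, 11/18 and 11/19 events. The overall rate is (1 − f)·0.105 + f·q.

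| | f = 1% | f = 2% | f = 3% |
|---|---|---|---|
| False-positive rate at 19.5% | 4.3% | 3.9% | 4.4% |
| Power, q = 19.5% | 86.3% | 84.7% | 87.2% |
| Power, q = 50% | 83.5% | 78.5% | 78.3% |

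**The case against.** The strongest reply is that the plan already handles most of this. The general statements promise 9-month follow-up to all treated subjects. The tipping-point analysis is mandatory and runs from worst to best case. A worst-case analysis is available where missingness looks intervention-related, the Kaplan-Meier analyses use time to day 30, and the list of causes in Section 6.6 need not be exhaustive. The group may also be empty.

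Much of this stands. It makes the point a conflict to be resolved rather than a proven absence of follow-up, and it limits the likely damage. It does not close the gap: the day-30 sentences are the more specific and would normally be followed at sites, and no sensitivity analysis can supply an outcome that was not collected.

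A reader might also infer more than the documents support:

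- *That everyone in both groups lacks a primary outcome.* Events by day 30 are still seen. Section 5.2.6 ends the index procedure at removal of the last guidewire, and TLR is a revascularization after the index procedure, so a later bypass might already count as TLR. The documents leave this open. Subjects who keep a study stent and have other treatment are followed in full.
- *That Section 5.2.3 shows how non-implantation arises.* Its dissection text concerns subjects who need more than two study stents and would normally already hold one. A dissection before device introduction is a screen failure under Section 5.2.1.
- *That the interim analysis cannot be triggered.* Section 6.8 accepts subjects who discontinued, and a day-30 exit can reasonably be read that way. Only the wording needs settling.

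**Conclusion.** The point holds as an unresolved conflict with a consequence for the primary analysis. If the specific day-30 sentences govern, ITT subjects without an implant, or with the stent explanted at bypass, who have no observed event by day 30 have no scheduled 9-month status for TLR, major amputation or restenosis. The complete-case condition cannot be assumed for them.

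The documents do not support saying that the test is biased towards success or that its error exceeds 5%. With half of the affected subjects having events, seven of the nine scenarios lie below 5% and three lie below the 3.65% design value. The results rest on assumed values of f, q and e and on the inferred complete-case rule. This should be fixed, because the omission is cheap to correct prospectively and may not be recoverable later; it does not invalidate the design.

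**What to change.** 1. Reconcile the Clinical Protocol Summary (Design, Procedures), Sections 2, 5.2.2, 5.2.4, 5.4 and 16, and footnote 1 of Appendix 1, so that every ITT subject has primary-endpoint ascertainment through 9 months: TLR, major amputation, and target-lesion duplex ultrasound where assessable. State in Sections 6.2 and 6.6 that these subjects enter the exact test with the observed outcome.
2. State whether a bypass conversion with explant counts as TLR, given where the index procedure ends.
3. In the tipping-point analysis, report any of these subjects still lacking 9-month status as a separate group, including the case in which all count as failures. This is a sensitivity result, not the decision rule.
4. State in Section 6.8 when such a subject counts as complete for the interim trigger.

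**Cost.** A few more 9-month assessments of a kind already in use, plus wording. Power may fall below 86.9% if these subjects do poorly: to about 83% at a 1% share and 78% at 3%, with half having events. The stated power should then be described as conditional on that share. In the scenarios computed, the false-positive rate stays below 5% once these subjects are in the denominator.
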